5.3 Concomitant Medications

- 5.3.1 Patients will be allowed to take supportive medications as needed. Anti-emetic medications should be used to treat nausea/vomiting at physicians' discretion.
- 5.3.4 G-CSF (Filgrastim and Neulasta) may be added for low ANC at treating physician's discretion.
- 5.3.5 Other concomitant medications and therapies deemed necessary for the supportive care and safety of the patient are allowed at the discretion of the treating physician.

5.4 Duration of Therapy

In the absence of treatment delays due to adverse events, treatment may continue until one of the following criteria apply:

- Disease progression as defined in Section 7.0 unless evidence of clinical benefit per the judgement of the treating clinician as per Section 5.5
- Inter-current illness that prevents further administration of treatment
- Unacceptable adverse event(s)
- Patient voluntarily withdraws from treatment **OR**
- General or specific changes in the patient's condition render the patient unacceptable for further treatment in the judgment of the investigator

5.5 Treatment Beyond Disease Progression

Subjects will be permitted to continue on treatment beyond RECIST v1.1 defined PD as long as they meet the following criteria:

- Investigator-assessed clinical benefit and do not have rapid disease progression
- Tolerance of study drug
- Stable performance status
- Treatment beyond progression will not delay an imminent intervention to prevent serious complications of disease progression (i.e. CNS metastases)

- Subject provides written informed consent prior to receiving any additional treatment with Carboplatin and Palbociclib, using an informed consent describing any reasonably foreseeable risk or discomforts, or other alternative treatment options.

The assessment of clinical benefit should take into account whether the subject is clinically deteriorating and unlikely to receive further benefit from continued treatment.

All decisions to continue treatment beyond initial progression must be documented in the study records. Subjects will be re-consented with an informed consent describing any reasonably foreseeable risks or discomforts.

Subjects should discontinue study therapy upon further evidence of further progression, defined as an additional 10% or greater increase in tumor burden volume from time of initial progression (including all target lesions and new measurable lesions).

New lesions are considered measurable at the time of initial progression if the longest diameter is at least 10 mm (except for pathological lymph nodes, which must have a short axis of at least 15 mm). Any new lesion considered non-measurable at the time of initial progression may become measurable and therefore included in the tumor burden measurement if the longest diameter increases to at least 10 mm (except for pathological lymph nodes, which must have an increase in short axis to at least 15 mm).

For statistical analysis that include the investigator-assessed progression date, subjects who continue treatment beyond investigator-assessed, response defined progression will be considered to have investigator-assessed progressive disease at the time of the initial progression event.

5.6 Off Treatment Criteria

Patients will be removed from protocol therapy when any of the criteria listed in Section 5.4 apply. Document in the source the reason for ending protocol therapy and the date the patient was removed from treatment. All patients who discontinue treatment should comply with protocol specific follow-up procedures as outlined in Section 5.6. The only exception to this requirement is when a subject withdraws consent for all study procedures or loses the ability to consent freely.

5.7 Duration of Follow-Up

Patients will be followed for survival until death. Patients removed from treatment for unacceptable adverse events will be followed until resolution or stabilization of the adverse event. End of treatment visit will be conducted within 30 days (+/- 5 days) of treatment discontinuation, however if patient refuses to present for a clinic visit, phone contact will be made within 30 days after study discontinuation of study treatment. Survival assessment can be done by phone and will be performed once every three months (+/- 1 month) until death.

5.8 Discontinuation Criteria

- 5.8.1** Disease progression with lack of investigator-assessed clinical benefit
- 5.8.2** Patient withdraws consent (termination of treatment and follow-up);
- 5.8.3** Loss of ability to freely provide consent through imprisonment or involuntary incarceration for treatment;
- 5.8.4** Patient is unable to comply with protocol requirements;
- 5.8.5** Treating physician judges continuation on the study would not be in the patients best interest;
- 5.8.6** Patient becomes pregnant (pregnancy to be reported along same timelines as a serious adverse event);
- 5.8.7** Lost to Follow-up. If a research subject cannot be located to document survival after a period of 1 year, the subject may be considered "lost to follow-up." All attempts to contact the subject during the one year must be documented;
- 5.8.8** Termination of the study by The University of Michigan or any other regulatory body

5.9 Patient Replacement

Patients enrolled but who do not receive protocol treatment will be replaced. Protocol treatment is defined as at least one dose of each drug.

6.0 STUDY PROCEDURES

6.1 Time and Events Table

6.1.1 Calendar

	Screening ¹	Treatment										Maintenance	Every 8 weeks from Cycle 7, Day 1	End of Treatment	Survival
		Cycle 1			Cycle 2		Cycle 3	Cycle 4	Cycle 5	Cycle 6	Cycle 7				
Day of Cycle		1	8	14	1	14	1	1	1	1	1	1	EOT ⁹	Survival ¹⁰	
Informed Consent	X														
Demographics	X														
Inclusion/Exclusion Criteria	X														
Tumor Biopsy for Correlative Analysis ¹⁴	X														
Interim Biopsy for Correlative Analysis ^{12,16}						X ³									
Tumor Biopsy to confirm progression ^{15,16}													X		
H&P, Relevant Medical History	X														
Pregnancy Test	X	X													
Clinic Visit ⁴	X	X		X ^{2,13}		X ^{2,13}	X								
Performance Status	X	X		X ^{2,13}		X ^{2,13}									
Physical Exam ⁴	X	X		X ^{2,13}		X ^{2,13}									
QOL Survey ⁴		X		X ^{2,13}		X ^{2,13}									
Adverse Effects Assessment ⁵		X		X ^{2,13}		X ^{2,13}	X								

	Screening ¹	Treatment										Maintenance		Every 8 weeks from Cycle 7, Day 1	End of Treatment	Survival
		Cycle 1			Cycle 2		Cycle 3	Cycle 4	Cycle 5	Cycle 6	Cycle 7	Cycle 8+				
Day of Cycle		1	8	14	1	14	1	1	1	1	1	1	EOT ⁹	Survival		
CBC ⁶	X	X		X ²	X ^{2,13}	X ²	X ^{2,13}		X							
CMP ⁶	X	X			X ^{2,13}		X ^{2,13}		X							
Correlative: Salivary Rinse ⁷		X	X ²		X ^{2,13}		X ^{2,13}									
Correlative: 2 Serum Tubes ⁷		X	X ²		X ^{2,13}		X ^{2,13}									
Correlative: 1 Serum Tube ⁷		x														
CT Imaging ⁸	X						X ³		X ³		X ³		X ³			
Palbociclib Dosing ¹¹		125 mg daily, days 1-14. Cycle Length: 21 Days										125 mg daily, days 1-21. Cycle Length: 28 Days				
Carboplatin Infusion		X			X		X	X	X	X						
Survival Assessment														X ¹⁰		

1= May be performed within 28 days of Cycle 1, Day 1 unless otherwise specified

2= May be performed +/- 4 days

3= May be performed +/- 7 days

4= Vital signs, physical exam, ECOG performance status will be checked at each visit as well administration of FACT H&N questionnaire (see Appendices B and C)

5= Toxicities will be evaluated using CTCAE version 4.03

6= Labs will be obtained pre-dose. CMP includes Basic Metabolic Profile (Na, K, Cl, CO2, BUN, Cr, Glu), AST/SGOT, ALT/SGPT, Alk Phos, T Bili, Albumin, Ca, and Total Protein

7= Collection tubes (see lab manual) will be drawn and sent to the [name] lab for DNA isolation and long term storage. May be performed +/- 4 days

8= CT Neck and Chest will be obtained in all patients. Further imaging (ie CT Abdomen/Pelvis, Bone Scan) will be performed as deemed appropriate by the treating physician. Initial staging imaging may be performed within 28 days prior to treatment

9= Will be performed within 30 days after discontinuation of study treatment. If the patient refuses to present for a clinic visit, phone contact will be made within 30 days after discontinuation of study treatment

10= Survival assessment can be done by phone and will be performed once every three months (+/- 1 month)

11= Will be administered orally on a daily basis, dose as defined per protocol

12=Biopsy at Cycle 2 will be offered if clinically safe and feasible. Patients may refuse repeat biopsy

13= In the event that the start of a new cycle is delayed due to treatment related toxicity, procedures required on Day 1 of the given cycle will be performed when palbociclib ± carboplatin is resumed. New Day 1 procedures that were performed prior to knowing the need to delay the start of the cycle do not need to be repeated 1) if not required to determine whether study drugs may be resumed and 2) if performed within 7 days prior to study drug resumption.

14= A biopsy demonstrating metastatic disease must be obtained within the 56 days prior to study treatment. FFPE core biopsy is preferred, however, if not clinically feasible or safe to obtain a core biopsy a block made from several FNA passes is acceptable. No systemic therapy (i.e. immunotherapy) may have been administered since obtaining the biopsy, if so, a new biopsy is needed.

15= If treating physician deems biopsy to be either unsafe or not clinically feasible, this must be documented and patient may forego repeat biopsy

16= FFPE core biopsy is preferred. However, if not clinically feasible or safe to obtain a core biopsy, contact coordinating site PIs ([name]) as a block made from several FNA passes is acceptable after PI approval.

7.0 MEASUREMENT OF EFFECT

7.1 Antitumor Effect- Solid Tumors

Response and progression will be evaluated in this study using the new international criteria proposed by the Response Evaluation Criteria in Solid Tumors (RECIST) Committee [EJC 45 (2009) 228-247]. Changes in only the largest diameter (unidimensional measurement) of the tumor lesions are used in the RECIST v1.1 criteria.

7.1.1 Definitions

Evaluable for toxicity. All patients will be evaluable for toxicity from the time of their first treatment with study drug.

7.1.2 Evaluable for response. Only those patients who have measurable disease present at baseline and have at least one dose of each drug will be considered evaluable for response. These patients will have their response classified according to the definitions stated below. In the case of death or disease progression before response classification, the outcome will be considered PD for calculation of disease control rate. Disease Parameters

Measurable disease. Measurable lesions are defined as those that can be accurately measured in at least one dimension (longest diameter in the plane of measurement is to be recorded) with a minimum size of:

- 10mm by CT scan (irrespective of scanner type) for studies with a slice thickness of ≤ 5 mm or twice the slice thickness or MRI
- 10mm caliper measurement by clinical exam (lesions which cannot be accurately measured with calipers should be recorded as non-measurable)
- 20mm by chest X-ray (if clearly defined and surrounded by aerated lung)

All tumor measurements must be recorded in millimeters (or decimal fractions of centimeters).

Malignant lymph nodes: To be considered pathologically enlarged and measurable, a lymph node must be ≥ 15 mm in short axis when assessed by CT scan (CT scan slice thickness recommended to be no greater than 5 mm). At baseline and in follow-up, only the short axis will be measured and followed.

Tumor lesions in previously irradiated areas are considered measurable if there has been progression in the lesion since completion of radiotherapy

Non-measurable disease. All other lesions (or sites of disease), including small lesions (longest diameter < 20 mm with conventional techniques or < 10 mm using CT scan), are considered non-measurable disease. Bone lesions, leptomeningeal disease, ascites, pleural/pericardial effusions, lymphangitis cutis/pulmonis, inflammatory breast disease, abdominal masses (not followed by CT or MRI), and cystic lesions are all non-measurable.

Target lesions. All measurable lesions up to a maximum of 2 lesions per organ and 5 lesions in total should be identified as **target lesions** and recorded and measured at baseline. Target lesions should be selected on the basis of their size (lesions with the longest diameter), be representative of all involved organ,

but in addition should be those that lend themselves to reproducible repeated measurements.

Lymph nodes merit special mention since they are normal anatomical structures which may be visible by imaging even if not involved by tumor. Pathological nodes which are defined as measurable and may be identified as target lesions must meet the criterion of a short axis of $\geq 15\text{mm}$ by CT scan. Only the short axis of these nodes will contribute to the baseline sum. The short axis of the node is the diameter normally used by radiologists to judge if a node is involved by solid tumor. Nodal size is normally reported as two dimensions in the plane in which the image is obtained (for CT scan this is almost always the axial plane; for MRI the plane of acquisition may be axial, sagittal or coronal). The smaller of these measures is the short axis. For example, an abdominal node which is reported as being $20\text{mm} \times 30\text{mm}$ has a short axis of 20mm and qualifies as a malignant, measurable node. In this example, 20mm should be recorded as the node measurement. All other pathological nodes (those with short axis $\geq 10\text{mm}$ but $< 15\text{mm}$) should be considered non-target lesions. Nodes that have a short axis $< 10\text{mm}$ are considered nonpathological and should not be recorded or followed. A sum of the diameters (longest for non-nodal lesions, short axis for nodal lesions) for all target lesions will be calculated and reported as the baseline sum diameters. If lymph nodes are to be included in the sum, then as noted above, only the short axis is added into the sum. The baseline sum diameters will be used as reference to further characterize any objective tumor regression in the measurable dimension of the disease.

Non-target lesions. All other lesions (or sites of disease) including pathological lymph nodes should be identified as non-target lesions and should also be recorded at baseline. Measurements are not required and these lesions should be followed as 'present', 'absent', or in rare cases 'unequivocal progression' (more details to follow). In addition, it is possible to record multiple non-target lesions involving the same organ as a single item on the case record form (e.g. 'multiple enlarged pelvic lymph nodes' or 'multiple liver metastases').

7.1.3 Guidelines for Evaluation of Measurable Disease

The same method of assessment and the same technique should be used to characterize each identified and reported lesion at baseline and during follow-up. Imaging based evaluation should always be done rather than clinical examination unless the lesion(s) being followed cannot be imaged but are assessable by clinical exam.

CT is the best currently available and reproducible method to measure lesions selected for response assessment. This guideline has defined measurability of lesions on CT scan based on the assumption that CT slice thickness is 5mm or less. When CT scans have slice thickness greater than 5 mm , the minimum size for a measurable lesion should be twice the slice thickness.

7.1.4 Response Criteria

7.1.4.1 Evaluation of Target Lesions

Complete Response (CR): Disappearance of all target lesions, determined by two separate observations conducted not less than 4 weeks apart. There can be no appearance of new lesions.

Partial Response (PR): At least a 30% decrease in the sum of the longest diameter (LD) of target lesions, taking as reference the baseline sum LD. There can be no appearance of new lesions.

Progressive Disease (PD): At least a 20% increase in the sum of the LD of target lesions (with a minimum absolute increase of 5 mm), taking as reference the smallest sum LD recorded since the treatment started, or the appearance of one or more new lesions.

Stable Disease (SD): Neither sufficient shrinkage to qualify for PR (taking as reference the baseline sum LD) nor sufficient increase to qualify for PD (taking as reference the smallest sum LD since the treatment started).

7.1.4.2 Evaluation of Non-Target Lesions

Complete Response (CR): Disappearance of all non-target lesions and normalization of tumor marker level.

Incomplete Response/Stable Disease (SD): Persistence of one or more non-target lesion(s) and/or maintenance of tumor marker level above the normal limits.

Progressive Disease (PD): Appearance of one or more new lesions and/or unequivocal progression of existing non-target lesions.

7.1.4.3 Evaluation of Best Overall Response

The best overall response is the best response recorded from the start of the treatment until disease progression/recurrence (taking as reference for progressive disease the smallest measurements recorded since the treatment started). The patient's best response assignment will depend on the achievement of both measurement and confirmation criteria.

Target Lesions	Non-Target Lesions	New Lesions	Overall Response	Best Response for this Category Also Requires:	
CR	CR	No	CR	>4 wks. confirmation	
CR	Non-CR/SD	No	PR	>4 wks. confirmation	
PR	Non-PD	No	PR		
SD	Non-PD	No	SD	documented at least once >4 wks. from baseline	
PD	Any	Yes or No	PD	no prior SD, PR or CR	
Any	PD*	Yes or No	PD		
Any	Any	Yes	PD		
* In exceptional circumstances, unequivocal progression in non-target lesions may be accepted as disease progression.					
Note: Patients with a global deterioration of health status requiring discontinuation of treatment without objective evidence of disease progression at that time should be reported as					

“*symptomatic deterioration*”. Every effort should be made to document the objective progression even after discontinuation of treatment.

Note: If subjects respond to treatment and are able to have their disease resected, the patient's response will be assessed prior to the surgery.

7.1.5 Duration of Response

Duration of overall response: The duration of overall response is measured from the time measurement criteria are met for CR or PR (whichever is first recorded) until the first date that recurrent or progressive disease is objectively documented (taking as reference for progressive disease the smallest measurements recorded since the treatment started).

The duration of overall CR is measured from the time measurement criteria are first met for CR until the first date that recurrent disease is objectively documented.

Duration of stable disease: Stable disease is measured from the start of the treatment until the criteria for progression are met, taking as reference the smallest measurements recorded since the treatment started.

7.1.6 Progression-Free Survival

Progression-free survival (PFS) is defined as the duration of time from start of treatment to time of progression.

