1.0 BACKGROUND AND RATIONALE

1.1 Disease Background

Head and neck squamous cell cancer (HNSCC) is the sixth most common cancer worldwide. Despite the prevalence of this disease, a significant proportion of patients progress despite appropriate therapy in which case treatment is palliative in intent. Unresectable recurrent or metastatic (R/M) HNSCC has a dismal survival and development of novel therapeutics has been met with little success.

Platinum compounds historically are the backbone of first line therapy however documented response rates to cytotoxic chemotherapy range between 10-30% with single agent regimens and 20-40% for multi-drug regimens. Although increased response rates are seen with doublet regimens, progression free survival (4.2-5.1 months) and overall survival (5.7-6.6 months) have not been significantly increased with the addition of further cytotoxic agents²⁻⁴. To date, the regimen associated with the best survival outcomes in the first line setting are seen with the use of a triplet consisting of cetuximab, a platinum, and 5-fluorouracil (the 'EXTREME' regimen'). In a sentinel publication when compared to platinum plus 5-fluorouracil, the EXTREME regimen resulted in improved overall survival (10.1 vs 7.4 months) and response rate (36 vs 20%). However this aggressive regimen is accompanied by significant rates of serious toxicities significantly limiting its use⁵. Given issues with toxicities and the baseline mediocre performance status at diagnosis, many patients with R/M HNSCC are not candidates for the EXTREME triplet regimen. Therefore, novel therapeutic approaches are necessary.

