2.3.2 Secondary Endpoints

- 2.3.2.1 Adverse events will be evaluated by clinical evaluation as well as routine lab work. Toxicities will be assessed via CTCAE v 4.03.

2.3.2.2 Survival endpoints to be assessed will include both overall survival and progression free survival time

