11.3 Data Analyses Plans

Disease control will be defined by RECIST v1.1 criteria at 12 weeks. CR, PR or SD will be considered disease control. The initial DCR rate with 95% confidence interval (CI) will be reported to give a point estimate and precision of the estimate at the conclusion of the trial. The number and proportion of adverse events will be reported by grade according to CTCAE version 4.03 guidelines. Progression free and overall survival time will be estimated using a Kaplan-Meier analysis.

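### Section 7.1.6 does not count death as a PFS event, so followed literally the endpoint is time to progression under the name PFS

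*Combined protocol and SAP*

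**What the plan says.** PFS is a secondary endpoint. Section 2.3.2 (Secondary Endpoints, under 2.4) states: "Survival endpoints to be assessed will include both overall survival and progression free survival time". Its definition is in Section 7.1.6: "Progression-free survival (PFS) is defined as the duration of time from start of treatment to time of progression". The analysis is in Section 11.3: "Progression free and overall survival time will be estimated using a Kaplan-Meier analysis". That section lists no events and gives no censoring rule.

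Four other places bear on the definition:

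- **Sections 7.1.4.1 and 7.1.4.2** define progressive disease by lesion growth, new lesions or unequivocal non-target progression. Death is not part of it.
- **Section 7.1.2**, the paragraph on evaluability for response, does count death: "In the case of death or disease progression before response classification, the outcome will be considered PD for calculation of disease control rate".
- **Section 5.5** dates progression for patients treated beyond it, who "will be considered to have investigator-assessed progressive disease at the time of the initial progression event". It is silent on death.
- **Section 7.1.5**, next to the PFS definition, uses the same form for duration of stable disease: "Stable disease is measured from the start of the treatment until the criteria for progression are met".

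Deaths are recorded. Section 5.7 states: "Patients will be followed for survival until death".

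**The concern.** The name of the endpoint and its definition disagree. Progression-free survival normally fails at progression or death, whichever comes first. A duration that ends only at progression is time to progression, and a patient who dies without documented progression never has an event.

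Such deaths are foreseeable here. Enrolment allows ECOG 2 and requires a life expectancy of only 12 weeks (Section 3.1). Section 7.1.4.3 provides for patients who stop treatment through global deterioration without objective progression. After treatment ends, survival contact may be by phone every three months (Section 5.7). None of this says how many such deaths there will be, but zero cannot be presumed.

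The trial has one arm and a historical reference (synopsis), so readers are likely to set its PFS beside outside figures, with no concurrent arm analysed under the same definition. What is at stake is that comparison. No decision rule uses PFS.

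**Working it through.** **1. Does any text repair the definition?** Take a patient who dies before response classification with no documented progression.

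| Rule | Outcome for this patient |
|---|---|
| DCR (7.1.2) | Counted as progressive disease, so a failure |
| PFS (7.1.6), read literally | No progression, so no event |
| Kaplan-Meier (11.3) | No event or censoring rule given |
| Treatment beyond progression (5.5) | Does not apply |

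The same death is a failure for the primary endpoint and not an event for PFS. Nothing closes the gap.

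**2. The plan's own figures.** None is stated for PFS. The only design figures are for DCR (Sections 11.1 and 11.2): 18 patients then 22, continue with 9 or more, promising with 21 or more of 40, stated type I error 0.059 and power 0.80. The exact check is the sum over x = 9 to 18 of P(X1 = x) × P(X2 ≥ 21 − x), with X1 ~ Bin(18, p) and X2 ~ Bin(22, p).

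- p = 0.40 gives 0.0593.
- p = 0.60 gives 0.8001.

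Both agree with the plan, and neither uses the PFS definition.

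**3. Direction.** Suppose deaths without progression are censored on the death date. At each time t with n patients at risk, the progression-only and progression-or-death analyses share the same n. The Kaplan-Meier factors are 1 − (progressions)/n and 1 − (progressions + deaths)/n. The first is never smaller, so the progression-only curve equals or lies above the other.

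The ordering can fail if deaths are censored at the last scan. Let patient A have a last scan at week 6 and die at week 20, and let patient B progress at week 12. With A censored at week 6, only B is at risk at week 12 and the progression-only curve falls to 0. The progression-or-death curve is 0.5 from week 12 until week 20.

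**4. Size, as an illustration.** Assumptions: constant independent hazards, progression observed continuously, deaths censored on the death date. Let m be the progression-or-death median and f the share of first events that are deaths without documented progression. The total hazard is ln 2 / m and the progression hazard is (1 − f) ln 2 / m, so the progression-only median is m / (1 − f). For scale, m is set to each end of the PFS range in Section 1.1 (4.2 and 5.1 months), treated as medians that count deaths. That treatment is also an assumption.

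| f (assumed) | 1/(1 − f) | m = 4.2 becomes | m = 5.1 becomes |
|---|---|---|---|
| 0 | 1.00 | 4.2 | 5.1 |
| 10% | 1.11 | 4.7 | 5.7 |
| 20% | 1.25 | 5.3 | 6.4 |
| 30% | 1.43 | 6.0 | 7.3 |

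**5. Against sampling error.** With 40 events and an exponential median of 4.2 months, an approximate 95% interval is 4.2 × exp(±1.96/√40), or 3.1 to 5.7 months. A shift at f of 20% or less lies inside it. The shift is systematic, however, and more patients would not remove it.

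**The case against.** The best defence is that this is drafting shorthand. The endpoint carries the word survival, Section 2.3.2 lists it among survival endpoints, and Section 7.1.2 shows that the authors count death as failure where they address it. No section says that deaths will be censored. This stands as evidence of probable intent and limits the weight of the point. It does not repair the text: Section 7.1.6 says what PFS is, and the death rule is expressly confined to DCR.

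The stakes are also low, and this stands in full. PFS has no hypothesis, threshold or power.

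The multipliers are fairly criticised too. The value of f is assumed, and progression will mostly be found at scans every two 21-day cycles (6 weeks), then every 8 weeks in maintenance. The observed median will therefore move in steps: it may not move at all, or it may jump by more than the table shows.

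Two stronger readings are tempting, and the documents support neither:

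- **That the historical figures show deaths before progression to be common.** A reader might infer this because PFS and overall survival lie close together in Section 1.1. That section gives two unpaired ranges, 4.2 to 5.1 and 5.7 to 6.6 months, and does not call them medians. The gap could be anything from 0.6 (5.7 − 5.1) to 2.4 months (6.6 − 4.2). A gap between PFS and survival does not estimate f in any case.
- **That reported PFS will certainly be too long.** This follows only if the literal rule is applied, such deaths occur, and they are censored on the death date.

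**Conclusion.** The definition in Section 7.1.6 is wrong as written for an endpoint called PFS. It omits death, and no other text supplies it. Followed literally, a named secondary efficacy endpoint would be time to progression under the wrong label.

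The direction is certain only under death-date censoring, where the curve equals or exceeds true PFS. The size cannot be computed, because f is not in the documents; the factor of 1.11 to 1.43 for f of 10% to 30% is an illustration under the assumptions of step 4. The conclusion rests on the text and not on those multipliers.

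The consequence is confined to one descriptive endpoint. The primary DCR, the two-stage rule and overall survival do not depend on it. The point should be corrected before analysis, so that the event rule is not chosen after the data are seen.

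**What to change.** Replace the sentence in Section 7.1.6 with a definition of PFS as time from start of treatment to the first of RECIST v1.1 progression or death from any cause, with patients alive and progression-free censored at their last evaluable tumour assessment.

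The cost is one sentence. Death dates are already collected under Section 5.7, so no new data are needed to count them.

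There are two downsides. Reported PFS may be shorter. Also, the calendar in Section 6.1 shows no CT after end of treatment, although Section 7.1.4.3 asks for efforts to document progression after discontinuation. Some deaths will therefore count as events after a gap in imaging in which progression may have gone unseen. A sensitivity analysis that handles deaths after such a gap differently would show how far the result depends on them.
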